8.7 Premature termination of the study

If all of the first three participants fail to reach the first level of BCI performance, being supervised use ([Section 8.1.1](#)), within 6 months after implantation ([Section 2](#)), and convincing solutions for future participants cannot be conceived, we will consider terminating the study prematurely (in consultation with DSMB). In addition, if a serious adverse device effect is reported for two subjects, we will consider terminating the study prematurely (in consultation with the DSMB).

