9. SAFETY REPORTING

9.1 Section 10 WMO event

In accordance to section 10, subsection 1, of the WMO, the investigator will inform the subjects and the reviewing accredited METC if anything occurs, on the basis of which it appears that the disadvantages of participation may be significantly greater than was foreseen in the research proposal. The study will be suspended pending further review by the accredited METC, except insofar as suspension would jeopardize the subjects' health. The investigator will take care that all subjects are kept informed.

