9.2.2 Serious adverse events (SAEs)

A serious adverse event is any untoward medical occurrence or effect that:

- results in death;
- is life threatening (at the time of the event);
- requires hospitalisation or prolongation of existing inpatients' hospitalisation;
- results in persistent or significant disability or incapacity, other than the existing disability of the patient;
- is a congenital anomaly or birth defect;
- Any other important medical event that may not result in death, be life threatening, or require hospitalization, may be considered a serious adverse experience when, based upon appropriate medical judgement, the event may jeopardize the subject or may require an intervention to prevent one of the outcomes listed above.

All SAEs will be reported through the web portal *ToetsingOnline* to the accredited METC that approved the protocol, within 15 days after the sponsor has first knowledge of the serious adverse reactions. SAEs will also be reported to the Clinical Representative of the funding agency (NIDCD).

SAEs that result in death or are life threatening should be reported expedited. The expedited reporting will occur not later than 7 days after the responsible investigator has first knowledge of the adverse reaction. This is for a preliminary report with another 8 days for completion of the report.

Notably, (scheduled) hospitalization for reasons of standard care and maintenance of invasive ventilation or other medical technology the participants may use will not be considered an SAE.

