9.2.3 Serious Adverse Device Effects (SADEs)

Adverse device effects are all untoward and unintended responses to an investigational device.

Unexpected adverse device effects are SADEs if the following three conditions are met:

1. the event must be serious (see chapter 9.2.2);
2. there must be a certain degree of probability that the event is a harmful and an undesirable reaction to the medicinal device under investigation;
3. the adverse reaction must be unexpected, that is to say, the nature and severity of the adverse reaction are not in agreement with the device information as recorded in the IMDD.

The sponsor will report expedited the following SADEs through the web portal

ToetsingOnline to the METC:

- SADEs that have arisen in the clinical trial that was assessed by the METC;
- SADEs that have arisen in other clinical trials with the same medical device, and that could have consequences for the safety of the subjects involved in the clinical trial that was assessed by the METC.

The remaining SADEs are recorded in an overview list (line-listing) that will be submitted once every half year to the METC. This line-listing provides an overview of all SADEs from the medical device, accompanied by a brief report highlighting the main points of concern. The expedited reporting of SADEs through the web portal *ToetsingOnline* is sufficient as notification to the competent authority.

The sponsor will report expedited all SADEs to the competent authorities in other Member States, according to the requirements of the Member States.

The expedited reporting will occur not later than 15 days after the sponsor has first knowledge of the adverse reactions. For fatal or life threatening cases the term will be maximal 7 days for a preliminary report with another 8 days for completion of the report.

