9.5 Data Safety Monitoring Board (DSMB)

A Data Safety Monitoring Board will be established for this study. It will perform online safety surveillance and performs interim analyses on the safety data. It will consist of a committee

whose members are independent from the research group. The DSMB will consist of experts in the areas of this research, including neurology, implantable devices and ethics.

The task of the DSMB will be to monitor the progress in the study in terms of achieving the stated objectives and improvement of the listed parameters for BCI signal processing. The DSMB meets before the study starts or early in the course of the study, to discuss the protocol, the study, any analysis plan, future meetings, and to have the opportunity to clarify any aspects with the principal investigators. After that, the DSMB will meet at least once a year. Additional meetings may be planned depending on timing of inclusion of patients and progress. One of the (regular or additional) meetings will be scheduled shortly after the first patient has been followed for six months after implantation. The DSMB will be asked to give advice at the decision moment after the third implantation, as to how to proceed based on the obtained results. It is the responsibility of the DSMB to verify adherence of the research team with the procedures as described in the research protocol.

The recommendations of the DSMB are circulated and approved by all DSMB members, then forwarded to the PI and, if deemed necessary, to the Ethics Committee of the UMC.

Criteria for decision to terminate the study prematurely

The key criterion for premature termination of the study (also stated in Sections 4.4, 8.7 and 10.4) is level of proficiency at 6 months after implant ('futility'). In addition the usual criteria are relevant, being unexpected problems with function of the device, unexpected systematic side effects that cause concern ('safety'). In addition the DSMB may decide to advise termination of the pilot study if results are above expectations (i.e. high levels of proficiency in all three first participants, 'positive efficacy'), to expedite a larger clinical trial.

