11.4.3 Surgery

The experiments involve a surgical procedure with implantation of electrodes underneath the skull, lead wires under the skin from the head to the chest, and/or positioning of a medical device under the skin on the chest. This procedure is the same as for deep-brain stimulators, but with a less invasive electrode positioning as they do not penetrate brain tissue (deep-brain stimulators travel through much of the brain white matter to reach their goal in the thalamus). Medtronic has already delivered 85.000 DBS stimulators for implantation in Parkinson patients alone, indicating that implantation of the device is by now a standard procedure.

* Because electrodes are already in place, imaging, electrode placement surgery and strip selection procedures are not relevant for new participants with existing implant.

The surgical implantation procedures (implantation of the electrodes and implantation of the Activa PC+S device) carry the same risks associated with any other brain surgery. In the worst case, risks of brain surgery may include serious complications such as coma, bleeding inside the brain, seizures and infection. Some of these may be fatal. However, the chance that complications occur is very low, among others since electrodes do not penetrate the cortex. The risk of subdural or epidural hemorrhage ranges from none to 2%. This literature is mostly based on devices penetrating the cortex (Bronstein et al., 2011; Franzini et al., 2011). Once implanted, the system may become infected. The risk of intracranial infection after implantation surgery is around 5% in the literature. The risk of infection at the abdomen where the cables are externalized is likely smaller.

Depending on the severity and the location of the infection, parts of the system may have to be explanted. After implantation, parts may wear through the skin, and the lead or lead/extension connector may move. Any of these situations may require additional surgery.

Notably, having two brain surgeries close together in time is standard clinical practice in the treatment of severe intractable epilepsy and other conditions, and does in itself not add any additional risks.

Risks related to the explantation scenarios ([see Section 8.3.14](#)) include infection (~3%) and, in the case of explantation of all implanted parts (including the electrodes), subdural or epidural hemorrhage (0-2%).

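### The two-subject safety rule in section 8.7 may leave out foreseen serious complications of implantation, because the only visible definition of the counted event is limited to unexpected device reactions

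*Combined protocol and SAP*

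**What the plan says.** Section 8.7 gives two grounds for considering early termination. One is futility in the first three participants. The other is safety: "if a serious adverse device effect is reported for two subjects, we will consider terminating the study prematurely", again in consultation with the DSMB. It does not define the event and does not refer to another section.

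The term is defined only in section 9.2.3. That section starts with a broad notion of an adverse device effect (any untoward, unintended response to the device) and then sets three conditions for a SADE. The event must be serious, it must with some probability be a reaction to the device, and, as the third condition puts it, "the adverse reaction must be unexpected, that is to say, the nature and severity of the adverse reaction are not in agreement". The yardstick for that comparison is the IMDD.

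The DSMB's safety grounds for advising termination, in section 9.5, use the same qualifier: "being unexpected problems with function of the device, unexpected systematic side effects that cause concern". Section 9.5 does not repeat the two-subject count.

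Section 11.4.3 sets out what is foreseen: "risks of brain surgery may include serious complications such as coma, bleeding inside the brain, seizures and infection. Some of these may be fatal". It puts intracranial infection after implantation at around 5%, and on bleeding it says "The risk of subdural or epidural hemorrhage ranges from none to 2" per cent.

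Three other safeguards bear on the point. Section 9.1 suspends the study pending METC review when "it appears that the disadvantages of participation may be significantly greater than was foreseen in the research proposal". Section 9.2.2 sends every SAE to the METC within 15 days, or 7 days for a preliminary report if fatal or life-threatening, and also to the funder's clinical representative. Section 9.5 says of the DSMB: "It will perform online safety surveillance and performs interim analyses on the safety data".

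**The concern.** The serious harms the protocol itself names for this trial are complications of placing subdural strips and a chest device. A counted safety rule in a five-person implant study would be expected to include them. If the definition in 9.2.3 governs 8.7, it can leave them out in two ways. A complication listed in the IMDD fails the unexpectedness condition. A complication put down to the operation rather than the device fails the device-reaction condition. The criteria in 9.5 do not close the gap, since they too are limited to what is unexpected.

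Two of five participants with a serious complication would be 40%, against the 5-7% that 11.4.3 implies for infection and haemorrhage. The sponsor and the DSMB should review such a result together before more people are implanted. Whether it triggers the rule should not depend on how one event is classified.

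**Working it through.** The plan states no operating characteristics for the two-subject rule, so there is no figure to reproduce. The check has two parts.

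**1. What counts under each reading of 8.7**

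| Serious event in two participants | 9.2.3 definition applied | Plain words of 8.7 | Proposed wording |
|---|---|---|---|
| Device reaction not foreseen in the IMDD | counts | counts | counts |
| Device reaction foreseen in the IMDD | does not count | counts | counts |
| Complication attributed to the surgery, not the device | does not count | arguable | counts |

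The second and third rows are where the complications in 11.4.3 may fall. Which of them are foreseen depends on the IMDD.

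**2. Scale, for two complication types only**

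Inputs from 11.4.3: intracranial infection about 5%, haemorrhage 0-2%. Treated as mutually exclusive, the risk per electrode surgery is p = 5% to 5% + 2% = 7%. Participants are taken as independent, with one electrode surgery each, and every such event is taken as serious.

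P(two or more of five) = 1 − (1−p)^5 − 5p(1−p)^4

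- p = 0.05: 1 − 0.7738 − 0.2036 = 0.0226, or 2.3%
- p = 0.07: 1 − 0.6957 − 0.2618 = 0.0425 (0.04249 before rounding), or 4.2%

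If infection and haemorrhage are instead independent, p = 1 − 0.95 × 0.98 = 0.069 and the upper figure is 4.1%.

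If the true risk of these events were higher (assumed values, not in the documents):

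- p = 0.20: 1 − 0.3277 − 0.4096 = 0.2627, or 26.3%
- p = 0.30: 1 − 0.1681 − 0.3602 = 0.4718 before rounding, or 47.2%

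On the literal reading, to the extent these events are foreseen in the IMDD or attributed to surgery, they add zero to the count at every value of p.

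A participant with an existing implant skips the electrode surgery. With four electrode surgeries, P(two or more) = 1 − (1−p)^4 − 4p(1−p)^3, which gives 1.4% at p = 0.05 and 2.7% at p = 0.07.

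Against the foreseen risk, 2/5 = 40%; 40/7 = 5.7 and 40/5 = 8, so about 6 to 8 times.

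**The case against.** The strongest reply is that the narrow reading is optional. Section 8.7 uses ordinary words, omits any reference to unexpectedness and does not cite 9.2.3, whose three conditions serve expedited reporting. On a plain reading, 8.7 covers any serious response to the device, foreseen or not. Even on the narrow reading, what is unexpected is decided by the IMDD, not by 11.4.3. This stands, and it is why the point says *may not count*. It does not remove the ambiguity: 9.2.3 is the only visible definition, and events attributed to surgery remain arguable on either reading.

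The second reply is that 9.1 is already stronger. It has no two-subject minimum and no unexpectedness filter, and it suspends the study where 8.7 only asks the team to consider stopping. Nothing makes 8.7 the exclusive ground. This also stands and limits the consequence. But 9.1 rests on a judgement that harm exceeds what was foreseen, and its review goes to the METC. The joint review with the DSMB comes from 8.7.

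A reader might infer from 9.2.2, which names the METC and the funder but not the DSMB, that the DSMB does not see SAEs. The documents do not support that. Section 9.5 gives the DSMB safety surveillance, which presupposes safety reports. Section 8.3.15 says that data after the end of participation are not monitored by the DSMB, which implies that data during participation are. The text of section 9.6 and any DSMB charter were not available to me. What remains is a missing detail in 9.2.2.

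**Conclusion.** The point holds as one of wording. Read literally, the plan's only counted safety rule can omit serious complications that 11.4.3 foresees, or that are attributed to surgery, even when two of five participants have them. It should be corrected, with medium confidence, because the outcome turns on an IMDD I have not seen and on how the sponsor meant 8.7 to be read.

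A reader might go further and conclude that the trial lacks safety oversight. It does not: suspension under 9.1, METC reporting of all SAEs and DSMB surveillance apply whichever way 8.7 is read.

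A reader might also take 2.3-4.2% as the rate at which a widened rule would be triggered. It is not. That range covers only intracranial infection plus haemorrhage at 5-7% per electrode surgery. The haemorrhage literature is mostly on cortex-penetrating devices, so it leans high for those two events. For the widened rule as a whole it is too narrow: it leaves out seizures, infection at other sites, the second operation, and skin erosion or lead movement needing further surgery. The documents give no combined risk from which the true rate could be worked out.

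**What to change.** In section 8.7, and repeated in 9.5, state that any serious event related to the implant surgery or the device, expected or not, counts toward the two-subject review with the DSMB. If the broad reading was always intended, this sentence records it.

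Optionally, as a clarification, name the DSMB in 9.2.2 as a recipient of these SAEs.

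The change needs protocol wording and no new committee. Its downside is that the review may be triggered somewhat more often, including for expected complications. As an illustration only, an assumed overall risk of related serious events of 12% or 15% per participant gives two or more of five in 11.2% (1 − 0.5277 − 0.3598) or 16.5% (1 − 0.4437 − 0.3915) of trials. Because the rule only asks that termination be considered, each trigger leads to a discussion, not a stop.

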9. SAFETY REPORTING

9.1 Section 10 WMO event

In accordance to section 10, subsection 1, of the WMO, the investigator will inform the subjects and the reviewing accredited METC if anything occurs, on the basis of which it appears that the disadvantages of participation may be significantly greater than was foreseen in the research proposal. The study will be suspended pending further review by the accredited METC, except insofar as suspension would jeopardize the subjects' health. The investigator will take care that all subjects are kept informed.

9.2 AEs, SAEs and SUSARs

9.2.1 Adverse events (AEs)

Adverse events are defined as any undesirable experience occurring to a subject during the study, whether or not considered related to the experimental intervention. All adverse events reported spontaneously by the subject or observed by the investigator or his staff will be recorded. All adverse events related to the Medtronic products will be reported to Medtronic.

